## 15.0 Potential Benefits\*

- *Describe the potential of any direct benefits that individuals may experience from taking part in the research. Include the probability, magnitude, and duration of the potential benefits as this will be useful to the IRB in making their risk/benefit determination.*

There may be no direct benefits to participating in this study. Some participants may benefit from learning about health information and care sources in their community.

- *Describe the potential of any benefits to society/science or others related to the possible knowledge gained.*

The knowledge gained from this study will help inform future local efforts aimed to connect teens in Kansas City to the healthcare they need and will inform the wider scientific/public health community of opportunities and effective strategies for integrating peer leader and mobile health intervention models.

## 16.0 Investigator Assessment of Risk/Benefits Ratio\*

**16.1 Please provide an assessment of risk and benefits in the table below. Note, the IRB makes the final determination based upon responses in the two preceding sections.**

Select as applicable:	Pediatric Risk Category:	
	Category 1	Research not involving greater than minimal risk (45 CFR §46.404 and 21 CFR §50.51)
	Category 2	Research involving greater than minimal risk but presenting the prospect of direct benefit to the individual subjects. (45 CFR §46.405 and 21 CFR §50.52)
	Category 3	Research involving greater than minimal risk and no prospect of direct benefit to individual subjects, but likely to yield generalizable knowledge about the subject's disorder or condition. (45 CFR §46.406 and 21 CFR §50.53)
	Category 4	Research not otherwise approvable which presents an opportunity to understand, prevent, or alleviate a serious problem affecting the health or welfare of children. (45 CFR §46.407 and 21 CFR §50.54)
Select if applicable:	Adult Risk Category:	
	Not Greater than Minimal Risk	
	Greater than Minimal Risk	

## **17.0 Payment, Reimbursement and Tangible Property provided to subjects\***

Is payment, reimbursement, or tangible property part of the study?

Yes       No (*If No, delete the following subsections*)

- **Payment to Subjects:** If providing payment for participation (e.g., cash equivalent for participation, payment for time off work), select the form of payment:

- Greenphire/ClinCard (will be used for in
- Gift Card: (Merchant: Rybbon electronic cards will be used as a primary compensation method. Physical Target/Walmart cards may be used for teens that prefer physical gift cards over electronic)
- Other: \_\_\_\_\_

*Note: "Gift Card" and "Other" options require approval by Research Administration. Upon submission in myIRB, ORI staff will initiate the Research Administration approval process.*

**Payment Schedule:** *Describe the payment schedule (if the payment schedule is involved, consider using a table to display this information) including:*

**Intervention Trial Participants:** Adolescents will have an opportunity to receive up to \$60. They will be given a \$30 gift card after completing the baseline survey. A \$10 gift card will be given for each follow-up survey that is completed at 2, 4, and 6 months after enrollment.

**Peer Leaders:** Teens can choose to earn an additional \$225 for being a peer leader or they can choose to earn up to 30 hours of academic volunteer or community service hours.

Teens that choose to earn an additional \$225 for being a peer leader will receive \$100 for Peer Leader Training, \$25 recruiting the first teens to the research study and \$ 5 for each teen recruited after the first teen (Maximum of \$50 for 10 additional friends enrolled), and they will get up to \$5 for each text message check-in or virtual meeting check-in (\$50 for up to 10 check-ins).

All Peer Leaders enrolled prior to protocol version 7.18.2022 will be contacted via phone and notified of compensation changes. The notification of change of compensation for Peer Leader participants will be documented in REDCap under the note section. For those who have already enrolled more than one friend will be retroactively compensated following the new compensation changes.

Teens can earn up to 30 hours of academic volunteer or community service hours for participating in the training, Peer Leader virtual meeting check-ins, helping study staff to prepare for events (inventory, setup and takedown), attending events, text message check ins, and recruiting other teens to enroll in the study.

For teens who choose academic volunteer or community service hours, they must follow the guidelines of their academic institutions to ensure the hours gained through AccessKCTeen 2.0 would count towards their requirement. If their academic institution does not allow the volunteer or community service hours, they have the option to join the research study and earn up to \$225 (as listed above) for their participation.

Teens will have the flexibility to change the type of compensation received, (up to \$225 or Academic Community Service Hours) at any time during the study.

**Event day Participants:** Adolescents will have an opportunity to receive study medications and/or testing. At demonstration events, they may receive emergency

contraception for future use. At clinical events, they may receive contraception (emergency contraception, depo-provera, birth control pills/patch) and/or testing for pregnancy/sexually transmitted infections.

- **Tangible Property:** If providing tangible property or any item of value given for participation (e.g., a toy, a tote bag, a water bottle, an electronic device), describe:
  - The item(s) to be offered to research participants at some of the mobile unit events include the following:
  - Demonstration event:

**Emergency Contraception Plan B (Levonorgestrel) for future use**

    - How and when will the item(s) be distributed

**This item will be given to any research participant who feels the need to have it after a mobile unit event (optional)**

    - The estimated total maximum value of the item(s).

**\$19**

    - Clinical event:
    - **Emergency Contraception Plan B (Levonorgestrel); birth control pills/patch/depot shot, testing for pregnancy and/or sexually transmitted infection.**
    - How and when will the item(s) be distributed

**These items will be given to any research participant who wants to start medication or get tested at a clinical event (optional)**

    - The estimated total maximum value of the item(s).

**Emergency contraception = \$19**

**birth control pills = \$78.80**

**birth control patch= \$113.60**

**depo shot= \$37.81**

**testing for pregnancy = \$15.26**

**testing for Chlamydia= \$115.33**

**Testing for Gonorrhea= \$24.69**

- *If the estimated total maximum value of payment and/or tangible property provided to an individual subject may exceed \$600, include plans for the collection of Social Security Number (SSN) or Individual Tax Identification Number (ITIN) per CM policy.*

## 18.0 Compensation for Research-Related Injury

4.

- *If the research involves more than Minimal Risk, describe the available compensation in the event of research related injury. NOTE: For industry sponsored studies, this must match the agreed upon language in the Clinical Trial Agreement (CTA).*

N/A

## 19.0 Economic Burden to Subjects

5.

- *Describe any costs that participants may be responsible for because of participation in the research. This may include transportation to appointments, time away from work, parking, additional lab tests, et cetera.*

N/A

## 20.0 Parental Permission and Adult Consent Process\*

**20.1** *Indicate below all methods of Permission/Consent that will be used in this study.*

- *If the study includes **multiple study groups**, be sure to indicate which method is being used with each group.*
- *If requesting a **Waiver of Documentation**, a complete **Waiver**, or an **Alteration**, complete the required regulatory addendum noted below.*

### **Waiver of Documentation of Permission/Consent**

Permission/Consent form provided but signature will **NOT** be obtained (e.g. verbal consent)

Must complete [\*\*Addendum A: Waiver of Documentation of Permission/Consent\*\*](#)

**Waiver of written documentation of permission of parent/LAR for pediatric participants** N/A

**Waiver of written documentation of consent of adult participants**

Study group(s) to which this method applies: We will obtain ***verbal*** consent for any participants who are aged 18 or older upon enrollment. This includes adolescents that may be 18 years and 364 old upon enrollment and adult stakeholder participants.

**Waiver of written documentation of consent of participants turning 18**

Study group(s) to which this method applies: (Active Participants) Any adolescent turning 18 during the study participation still actively participating in study activities. In the case a participant turns 18 from the time of the baseline survey through the time of the follow-up surveys, we will complete ***verbal*** adult informed with that participant before the 2, 4, 6-month follow-up call.

### **Waiver or Alteration of Permission/Consent**

Adult consent will **NOT** be obtained, or you propose to alter a required element of consent.

Must complete [\*\*Addendum B: Waiver of Permission/Assent/Consent\*\*](#)

**Waiver/Alteration of permission of parent/LAR for pediatric participants**

Study group(s) to which this method applies: All parents of adolescents between the ages of 14-17.

**Waiver/Alteration of consent of adult participants**

Study group(s) to which this method applies:

**Waiver of consent of participants turning 18**

Study group(s) to which this method applies: (Non-Active Participants) Adolescent participants that turn 18 during the study and have completed study activities for the continued access to and use of identifiable data.

## **Additional Methods**

**Obtaining permission/assent/consent of non-English speaking parents or participants**

**Must complete [Addendum C: Non-English Speaking Subjects](#)**

Study group(s) to which this method applies:

**Surrogate decision maker consent form adults not capable of consenting for themselves**

**Must complete [Addendum D: Surrogate Decision Maker Consent](#)**

Study group(s) to which this method applies:

**20.2 Permission/Consent/Consent at 18 Discussion:** *If selected options for “Written” or “Waiver of Documentation” above, describe below how the informed permission/consent discussion will be conducted. Describe:*

- *Where and when the discussion will take place.*
- *Steps that will be taken to minimize the possibility of coercion or undue influence.*
- *Any supplemental materials that will be used to enhance the discussion (e.g. videos, sent, educational pamphlets).*
- *Any measures that will be taken to ensure that parent(s)/LAR have adequate time to ask questions and decide if they will permit their child to participate in the study (e.g., providing a copy of permission form in advance of visit).*
- *How comprehension of the permission form will be verified (e.g. teach back).*
- *If obtaining permission via telephone, confirm CM research policy will be followed.*
- *Process to ensure ongoing consent during the study.*

## **Intervention Trial Participants:**

For adolescents, we will review a study information sheet in-person or online (*titled Study Information Letter for Intervention Participants*). This info sheet will be available for the participant to keep. We will use a teach-back method to ensure participant understanding and ensure that the participant has the opportunity to ask questions before agreeing to participate.

**20.3 Documentation of Permission/Consent/Consent at 18:** *If selected “Written” options above, explain how informed permission will be documented. Describe:*

- *Whether CM Research Policy “10.04 Obtaining Permission/ Assent/ Consent” and “Research Documentation in the Electronic Health Record” will be followed. If not, describe whether and how permission of the parent(s)/LAR will be documented in writing.*
- *Whether e-Consent will be used to document permission (non-FDA regulated studies only).*

N/A

**20.4 Identification of participants turning 18:** *Explain the process for tracking participants to ensure that consent is obtained to continue participation once they turn 18 years of age.*

**INTERVENTION TRIAL PARTICIPANTS:** We will build a REDCap alter to indicate to study staff on the Event Daysurvey (optional) and on the *Survey Measures Interventional Trial Participants* follow-up surveys whether the adolescent has turned 18 since the baseline survey according to their date of birth. If yes, we will proceed with adult consent processes and record having done so in the REDCap survey. If the participant attends a mobile unit event and has turned 18, they will be re-consented in-person at the event. If they have turned 18 by the follow-up surveys, they will be re-consented over the phone.

## **21.0 Assent of Pediatric Subjects**

**21.1 Select the option(s) that apply to the study:**

**Obtaining assent of pediatric participants is NOT POSSIBLE due to:**

- The capability of the participants (considering the ages, maturity, physical and/or psychological state) is so limited that they cannot reasonably be consulted.*
- The intervention or procedure involved in the research holds out a prospect of direct benefit that is important to the health or well-being of the participants and is available only in the context of the research.*

**Obtaining assent of pediatric participants is NOT PRACTICLE given the context of this study** (e.g., minimal risk, no direct contact with subjects).

**Must complete [Addendum B: Waiver/Alteration of Permission/Accent/Consent](#)**

**Assent of pediatric participants WILL BE SOUGHT following assessment of ability to assent: Waiver of written documentation of assent of pediatric participants (ages 14-17)**

**21.2 Assessment of Ability to Assent:** *If seeking assent from pediatric subjects, describe how the ability to assent will be determined.*

**Intervention Trial Participants:** Adolescents will have to be at least 14 years of age or older to participate. Study staff will determine ability to provide assent in similar manner as with adult consent.

**21.3 Assent Discussion:** *If seeking assent from pediatric participants, explain how the assent discussion will be conducted. Describe:*

- *Where and when the discussion will take place.*
- *Steps that will be taken to minimize the possibility of coercion or undue influence.*
- *Any age-appropriate supplemental materials that will be used to enhance the discussion (e.g., videos, eConsent, educational pamphlets).*
- *Any measures that will be taken to ensure that pediatric participants have adequate time to ask questions and decide if they want to participate in the study.*
- *How comprehension of the study will be verified (e.g., teach back).*
- *If obtaining assent via telephone, confirm CM research policy will be followed.*
- *Process to ensure ongoing assent during the study.*

The minor adolescents (ages 14-17) will be asked to provide **verbal** assent after the study is explained in detail in person. We will follow best practice guidelines established for adolescent participation in health research. This includes building a research team that is specially trained to work with adolescents, using age-appropriate language that is easy to understand and allowing adolescents ample time to consider participation and

ask questions. We will clearly state that participation is voluntary. Potential adolescents will be asked if they understood the information and if they have any questions.

For those adolescents who enroll virtually they will be provided with the study information sheet (titled Study Information Letter for Intervention Participants) from our REDCap to review by themselves. If the participant has any questions about the study, they can contact the PI listed on the information sheet or the research staff over the phone to ask questions prior to completing the study. If the adolescent does not have any questions about the study, they will use REDCap to agree to the study.

**21.4 Documentation of Assent or Inability to Assent:** *If seeking assent from pediatric participants, explain how assent, or a determination of inability to assent, will be documented. Describe:*

- *Whether CM Research Policy “10.04 Obtaining Permission/ Assent/ Consent” and “Research Documentation in the Electronic Health Record” will be followed. If not, describe whether and how assent, or inability to assent, will be documented in writing.*
- *Whether e-Consent will be used to document assent (non-FDA regulated studies only).*

For this mature group of minors (ages 14-17), we wish to document assent or inability to assent similarly to how we will document adult consent. Study staff conducting assent will document within REDCap that the participant indicated they understood all study procedures, had the ability to answer questions, and agreed to participate. However, we will not be collecting signatures.

## 22.0 HIPAA and Confidentiality

HIPAA regulations apply to this study if the data used or accessed relates to:

The past, present or future physical or mental health or condition of an individual; The provision of health care to an individual; OR The payment for the provision of health care.

## 22.1 HIPAA Authorization

*Select all applicable methods of HIPAA Authorization that apply to this study.*

- Full Written HIPAA Authorization will be obtained (within the p/a/c form or standalone form)
  
- Partial Waiver of HIPAA Authorization (e.g., waiver for recruitment and pre-screening purposes only)

**Must complete [Addendum E: Waiver/Alteration of HIPAA Authorization](#)**

- *Describe the PHI for which use, or access is necessary for research.*

- Alteration of HIPAA Authorization (some but not all required elements of an Authorization are present, e.g., signature will not be obtained)

**Must complete [Addendum E: Waiver/Alteration of HIPAA Authorization](#)**

- *Describe which proposed elements to be altered.*

We will not obtain a signature from adolescents

- Waiver of HIPAA Authorization (authorization will NOT be obtained)

- If Other, explain:

**22.2 Indicate how the research team will protect the confidentiality of subjects' data during storage, use, and transmission (e.g., training, authorization of access, password protection, encryption, physical controls, and separation of identifiers and data [master list]). Remember: Sensitive CM data, including research data, must be stored on a file server on the CM network domain – not on a workstation hard drive.**

We will store all data in REDCap on a CM secured device. Signatures on paper will not be obtained to avoid obtaining written PHI.

**22.3 State whether a Certificate of Confidentiality has been issued for this study. Certificates are automatically issued for NIH funded research per [NIH policy](#). For non-federally funded research involving identifiable, sensitive information, investigators may apply for a Certificate if desired. See the [NIH website on Certificates of Confidentiality](#) for more details.**

This study is funded by the NIH and therefore is automatically provided a certificate of confidentiality.

## **23.0 Provisions to Protect the Privacy Interests of Subjects\***

**23.1 Describe the steps that will be taken to protect subjects' privacy during recruitment and while obtaining permission/assent/consent. For example, best practice is to obtain permission/assent/consent in a separate area where a private conversation can be had. If this is not possible, be sure to explain what steps will be taken to provide as much privacy as possible.**

Assent/consent will be collected one-on-one in-person or virtually with all adolescents. For adolescents, study staff will make sure potential adolescent participants have access to privacy remotely or in-person.

**23.2 Describe what steps you will take to make the subjects feel at ease with the research situation in terms of the questions being asked and the procedures being performed. "At ease" does not refer to physical discomfort, but the sense of intrusiveness a subject might experience in response to questions, examinations, and procedures.**

Adolescents will be contacted by study staff with experience working with adolescent research participants. They will be told about the study and given as much time as necessary to decide if they want to participate. We will ensure that adolescents know they are free to choose whether to participate in all study-related activities and surveys.

**23.3 Indicate how the research team is permitted to access any sources of information about the participants and how the research team will protect the confidentiality of the data.**

We will input all survey data into REDCap that is on a secured server.

**24.0 Withdrawal of Subjects\***

*24.0 Describe anticipated circumstances under which participants will be withdrawn from the research without their consent.*

N/A

*24.1 Describe procedures that will be followed when participants are withdrawn from the research, including data retention plans or partial withdrawal from procedures with continued data collection.*

For adolescents that do not complete the follow-up surveys, we will still use their baseline data for analysis. Their contact information will be destroyed after the third attempt to reach them.

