#### **Research Interventions\***

#### **4. Description:**

- This intervention will examine the impact peer leaders have in mobilizing their networks to engage in health events and care for MH and SRH. We will examine intervention feasibility. We will examine our primary outcome through surveys.

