## 3. Recruitment of Potential Subjects:

### 1. Describe when, where, and how potential participants will be recruited.

INTERVENTION TRIAL PARTICIPANTS: Community organizations and partners will be given a paper or digital flyer (*titled Peer Leader Flyer*) about the program and see if any adolescents are interested. They will then let a study team member know which adolescents would like to be in the study. A study member will approach the interested adolescents to see if they would like to be a part of the study. After interested adolescents are enrolled, adolescents will turn to their social networks to recruit more adolescents to participate in the trial. After networks are formed, networks will nominate a peer leader to work with our team to disseminate health information related to SRH and MH.

A Children's Mercy social media account will be used in accordance to CMH requirements if needed to facilitate follow-ups for AccessKCTeen surveys, and to inform Peer Leaders of AccessKCTeen events for them to share with their peer networks for recruitment.

- a) ADOLESCENT INTERVENTION TRIAL PARTICIPANTS: We will develop a digital or paper flyer (*titled Peer Leader Flyer*) about participation in this research study that will be distributed to our community partners and enrolled adolescents.
  - o Adolescents will not be contacted more than three times for initial study participation. For each follow-up survey, study staff will make up to three attempts to reach these teens by phone, text (reminder of appointment for survey through Twilio/Spark or CM approved messaging), and/or email.
- b) ADOLESCENT EVENT PARTICIPANTS: We will recruit adolescents using paper or digital information sheets on the day of the event. We will create a QR code that community partners may share with potential participants. The text will read:

Get healthy with Children's Mercy!

We hope to talk with you about our study to learn about getting care on a mobile health unit. Your health and your voice matter!

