## 11.0 Follow-up

- c) **INTERVENTION TRIAL PARTICIPANTS:** Adolescents will interact with us for 6 months as this is the duration of the intervention period. After *enrollment*, adolescents will complete a follow-up survey at 2, 4, and 6 months. Study staff will make up to three

attempts to contact the participant and the follow-up survey will be administered via phone call, text message (Twilio/Spark) or Email.

d) *Event Day Participants: N/A*

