## 27.0 Data Analysis\*

8.

1. *Describe the data analysis plan, including any statistical procedures or power analysis.*

*Describe how the sample size for the study was determined (e.g. formal sample size calculation, convenience sampling). To minimize the risks associated with a possible breach of confidentiality, appropriate sample size calculations limit the amount of patient data being recorded to the amount necessary to answer the research question.*

Quantitative data: We will conduct descriptive analysis with inferential and graphical exploratory analytic techniques, presenting mean, median, and interquartile range [continuous variables] and frequency and percentage [categorical variables]. We will examine outliers and/or influential points, perform bivariate analyses to assess relationships, and summarize group data. We will use SAS 9.4 (SAS Institute Inc., Cary, NC, USA); the significance level will be 0.05. For our primary outcome, we calculate the proportion in each arm with any health care utilization at 6 months. We use logistic regression to assess intervention effect on utilization and explore differences in other outcomes. Models will include covariates to adjust for variables (e.g., sex, age) that may increase precision. We will explore heterogeneity of effects with stepwise addition on interaction terms to examine moderation by sex, age, or engagement. If >20% of data is missing, we will use complete cases or imputation, based on missingness pattern.

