Increasing Teen Access to Care (AccessKCTeen2)

NCT05444855

05 September 2023

Statistical analysis plan

We will use R software (R Foundation for Statistical Computing) for analyses. We will conduct descriptive analysis with inferential and graphical exploratory analytic techniques, presenting mean, median, and interquartile range [continuous variables] and frequency and percentage [categorical variables]. Next, bivariate analyses will be conducted to assess the relationship between variables. We will examine data for outliers and/or high leverage points and use established best practices in decided how to address them.

We will compare outcomes using independent t-tests for continuous variables and Chi-Square or Fisher's exact test for categorical variables depending on cell counts. If continuous variables are highly skewed nonparametric testing will be implemented (i.e., Wilcoxon rank-sum test). All tests will be two-sided, assessed with significance of $p<0.05$. We will evaluate these feasibility constructs:(acceptability, demand, implementation, practicality, integration, expansion, limited efficacy [see primary outcome]) using descriptive statistics. *Primary outcome:* We will calculate the proportion of adolescents with any health care utilization at 6 months.

Attrition: We will use established methods to minimize attrition (see "Recruitment and Retention") and plan to assess for our primary outcome every two months to keep participants engaged and minimize bias. Participants who are lost to follow-up after three attempts at 6 months will be excluded from the denominators for hypothesis testing. We will report on demographics of those lost to follow-up compared to those who completed the study.

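### Could the rule on destroying contact details after a third attempt cut teens off before the 6-month outcome survey?

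*Protocol*

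**What the plan says.** Protocol 24.1 answers a template question about procedures when participants are withdrawn. Its answer has two sentences: "For adolescents that do not complete the follow-up surveys, we will still use their baseline data for analysis", followed by "Their contact information will be destroyed after the third attempt to reach them". Neither says at which survey the third attempt is counted.

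The contact schedule is in two places. Protocol 8.0 (item 3, recruitment) says "For each follow-up survey, study staff will make up to three attempts to reach these teens by phone", and adds text and email as further routes. Protocol 11.0 says "adolescents will complete a follow-up survey at 2, 4, and 6 months", again with up to three attempts.

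The outcome depends on the last of these surveys. Protocol Research Interventions (item 4) says "We will examine our primary outcome through surveys". Protocol 27.0 says "For our primary outcome, we calculate the proportion in each arm with any health care utilization at 6 months". The SAP's attrition paragraph adds a "plan to assess for our primary outcome every two months to keep participants engaged and minimize bias", and defines the exclusion: "Participants who are lost to follow-up after three attempts at 6 months will be excluded from the denominators for hypothesis testing".

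**The concern.** Up to three attempts are made at each of three waves, so a third attempt can occur at month 2, month 4 or month 6. If staff applied 24.1 at the first wave a teen missed, the recorded phone number and email address would be gone before the 6-month survey. The teen could not then be approached by those routes when the primary outcome is measured, and deletion cannot be undone.

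The month-6 sample would then be selected on early responsiveness. Teens who answer early surveys may differ in care-seeking from those who do not, so the 6-month proportion could be biased. These teens would also fall outside the SAP's wording for loss to follow-up, since they would never receive three attempts at 6 months.

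**Working it through.** The documents give no non-response rate and no calculation on this point, so there is no stated figure to reproduce. The check has three parts.

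**1. Attempts kept under each reading.** Inputs: 3 surveys (Protocol 11.0) and up to 3 attempts per survey (Protocol 8.0). Planned attempts = 3 x 3 = 9.

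| Wave at which 24.1 is triggered | Attempts made | Attempts forgone | Month-6 attempts left |
|---|---|---|---|
| Month 2 | 3 | 9 - 3 = 6 | 0 of 3 |
| Month 4 | up to 3 + 3 = 6 | at least 3 | 0 of 3 |
| Month 6 | up to 9 | 0 | 3 of 3 |

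The choice of reading therefore matters, and the next step is to see which one the plan supports.

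**2. The passages side by side.**

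- Protocol 24.1 speaks of follow-up surveys in the plural and answers a question about withdrawal. Nowhere does the plan treat one missed survey as withdrawal.
- Protocol 8.0 gives every follow-up survey its own three attempts. Deletion after month 2 or 4 would make that instruction impossible to carry out by the listed routes.
- Protocol 25.0 (item 4) records names, phone numbers and email addresses for the 2-, 4- and 6-month calls. Addenda B and E justify holding contact data by the need to reach teens for the follow-up surveys.
- The SAP counts loss to follow-up only after three attempts at 6 months, which presupposes that contact details still exist then.
- Protocol 14.0 puts destruction at the end of the study. Protocol 28.0 puts it at study completion, or after 5 years for teens open to future research. Addendum E removes protected health information once the last contact has been made, and the last planned survey contact is at month 6.

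No passage calls for destruction at month 2 or 4.

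**3. What a misreading could do, as illustration only.** Assume non-response m at each wave, independent across waves. Month-6 missingness is m with a month-6 trigger and 1 - (1 - m)^3 with a trigger at any missed wave. N = 250 is the enrolment cap. It may include event-day participants, who have no follow-up, so the counts are upper-end.

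| Assumed m | Month-6 trigger | Any-wave trigger | Extra missing of 250 |
|---|---|---|---|
| 5% | 5.0% | 1 - 0.95^3 = 14.3% | about 23 |
| 10% | 10.0% | 1 - 0.90^3 = 27.1% | about 43 |
| 20% | 20.0% | 1 - 0.80^3 = 48.8% | 72 |

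The SAP's 20% threshold for imputation would be reached at m = 1 - 0.8^(1/3), about 7.2%. If the same teens miss every wave, the difference shrinks towards zero. These figures show how the result moves with the assumption and are not predictions.

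**The case for a change.** The strongest case for a change is that 24.1 is the section staff would consult on non-completers, it names no wave, and it does not refer to the SAP. Addendum E's reference to the last contact names no wave either. Deletion is irreversible, and one sentence would remove the doubt at little cost: details held 6 - 4 = 2 to 6 - 2 = 4 months longer than under the early reading.

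The textual point stands: 24.1 is silent on the wave. The consequence does not follow. Harm requires staff to adopt a reading that contradicts the attempt schedule in Protocol 8.0, and it requires those teens to be reachable at month 6. A complete loss of outcome data is also not certain even then. The feasibility table in Protocol 9.0 lists the study or medical record as a source for utilization, Protocol 25.0 ticks the medical record number as recorded, and Protocol 8.0 mentions a social media account for survey follow-up. Against that, Protocol 25.0 (item 2) says all data come directly from participants, so the documents do not settle whether another route could stand in.

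The analytic consequence is limited as well. Below 20% missing, the SAP deletes incomplete records list-wise in any case. Above 20%, the SAP imputes, while Protocol 27.0 allows either complete cases or imputation.

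A side issue is that 24.1 states no exception for the 5-year retention in Protocol 28.0. That is housekeeping with no effect on the estimate, and Addendum E partly covers it with a separate database for teens willing to be contacted again.

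**Conclusion.** No change is needed. Section 24.1 leaves out the wave, but read with Protocol 8.0, 14.0, 25.0 and 28.0, Addenda B and E and the SAP, it most plausibly means the third unsuccessful attempt at the 6-month survey. On that reading all 9 planned attempts remain possible, none is forgone, and no bias in the 6-month proportion follows from the plan.

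The conclusion assumes that staff read 24.1 together with the per-survey attempt schedule. If they did not, the effect would depend on non-response rates and on its persistence across waves, neither of which the documents give. Wording that named the 6-month survey would be harmless, but it would only restate what the rest of the plan already implies and would not alter the analysis or the primary estimate.
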